9.3 Early termination of the study

The leader of the project decides to stop or interrupt the study in advance in the case of force majeure, and should inform the doctors involved in the study in writing. Similarly, any participating unit that decides to withdraw from the study for any reason should also notify the project leader in written form.

9.4 Research, supervision and inspection

9.4.1 Research supervision

Inspectors must follow the drug clinical trial quality management specification (GCP) and standard operation procedures (SOP), visit the research unit regularly or according to the actual situation, supervise the clinical trial work and progress, check, confirm all data records and reports, correct and complete, consistent with the original data, ensure the clinical trial in accordance with the clinical trial protocol, the researchers should actively cooperate with the inspectors. The specific contents of the inspector include:

A) Ensure before the test that the test undertaking unit has appropriate conditions, including staffing and training, complete laboratory equipment and good operation, various inspection conditions related to the test, and estimated sufficient quantity. All the participants were familiar with the requirements in the test protocol;

B) Monitor the implementation of the trial protocol during the trial, confirm that the informed consent of all subjects is obtained before the trial, understand the enrollment rate of the subjects and the progress of the trial, and confirm that the selected subjects

are qualified;

- C) Confirm that the records and reports of all data are correct and complete, and that all case report forms are entered correctly and consistent with the original data. All errors or omissions have been corrected or indicated, signed and dated by the Investigator.
- D) Verify that all adverse events are recorded, and that serious adverse events shall be reported and recorded within the specified time;
- E) Clearly and truthfully record the failed visits, unconducted tests, and undone checks should be made, and whether the errors and omissions should be corrected;
- F) The written inspection report shall be completed after each visit, which shall state the date, time, name of the inspector, findings of the inspection, etc.

9.4.2 On-site inspection

The responsible unit may conduct an on-site inspection of the research at a clinical research institution. The audit includes the required test documents, records of the informed consent process, and the consistency of the eCRF and the original documents. But also the content and scope of the inspection can be increased according to the situation. The investigator agrees to participate at a reasonable time and in a reasonable manner.

10. Investigators' responsibilities

10.1 Participating physician responsibilities

The participating physicians will implement the study following the study protocol and confirm the accuracy of the data entered. The participating physicians should be responsible for obtaining written signed informed consent for data collection from the study subjects.

10.2 Responsibility of the project leader

The project leader takes all reasonable steps and provides sufficient resources to ensure the implementation of the research, mainly involving the following aspects:

- A) Ensure that the study complies with relevant national and local regulations, including ethical requirements, patient data protection regulations, etc.
- B) Ensure the effectiveness of quality control and analysis of research results.

11. Results sharing

The intellectual property rights, trial data and research results related to this anatomical study are jointly owned by the Nanjing First Hospital and the Department of Anesthesiology, and the University and the Anatomy Teaching and Research Section of Nanjing Medical University.

The intellectual property rights, trial data and research results related to this clinical study are owned by Nanjing First Hospital and the Department of Anesthesiology.

12. Data analysis

Data collection: It was collected by the same anesthesiologist who did not know the grouping situation.

Statistical analysis was performed using SPSS 22.0 software. Measurement data were expressed as mean \pm standard deviation ($X \pm s$), and comparisons between groups were conducted using the paired t-test. Categorical data were compared using the chi-square (χ^2) test, and ordinal data were compared using the rank-sum test. A

P-value of <0.05 was considered statistically significant.

13. Ethics principles and requirements for clinical research Clinical research will follow the world medical congress of the declaration of Helsinki and the national health and family planning commission of the People's Republic of China involving human biomedical research ethics review method and other relevant provisions, the specific implementation of informed consent, the privacy protection, research free and compensation, risk control, special subject protection and research related damage compensation principles and requirements.The clinical study was performed before the ethics committee approved the trial protocol.Before each subject is enrolled in the study, the investigator has the responsibility to present the subject or his legal agent about the purpose, procedures of the study and possible risks, and sign a written informed consent form that their participation in the clinical study is completely voluntary, that they may refuse to participate or withdraw from the study at any time at any stage of the trial without discrimination and retaliation, and their medical treatment and interests are not affected.The informed consent form should be retained as a clinical research document for future reference to effectively protect the subjects' personal privacy and data confidentiality.

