2.2 Study endpoint

2.2.1 Primary study endpoints

Percentage reduction in adductor muscle strength at 5, 10, 15, 20, 25, 30 minutes, and 3 hours post-administration.

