2.2.2.2. Safety study endpoint

1) Incidence of adverse reactions such as local anesthetic toxicity and nerve injury post-administration.

2) Procedure time and number of needle passes.

3. Expected results

Pericapsular nerve group (PENG) block is effective and safe in preventing obturator nerve reflex during transurethral resection of bladder tumors.

4. Design and method of the study

This clinical study uses a single-center, randomized, single-blind, parallel controlled trial design, divided into screening period, treatment period and follow-up periods.

4.1.1 Screening period:

Patients undergoing transurethral resection of bladder tumors signed informed consent forms for enrollment. Subjects who met all inclusion criteria and did not meet any exclusion criteria were randomized in a 1:1 ratio to the experimental and control groups, either one day before surgery or on the day of surgery.

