4.1.2 Treatment Period

Upon entering the operating room, HR, BP, ECG, and SpO₂ were monitored. Intravenous access was established, and oxygen was administered. Patients were randomly divided into two groups using a random number table: the pericapsular nerve group (PENG) block group (P group) and the obturator nerve block group (O group).

In the P group, patients were placed in the supine position, and the inguinal region was exposed, followed by routine disinfection and draping. A convex ultrasound probe (frequency 2-5 MHz) was positioned at the patient's inguinal ligament, with one end directed toward the anterior inferior iliac spine (AIIS), clearly visualizing the bony prominences of the iliopubic eminence and the AIIS. An out-of-plane technique was used, with the needle tip directed medially toward the pectenous muscle. Care was taken to avoid the femoral artery, vein, and nerve during needle insertion. Once the

needle tip reached the space between the pectineus muscle and the pubic bone, and after confirming no blood upon aspiration, 30 ml of 0.375% ropivacaine was injected. In the O group, patients were placed in the supine position, with the affected thigh abducted and externally rotated. The ultrasound probe was positioned at the inguinal ligament and moved medially to locate the adductor muscles and pectineus muscle. Care was taken to avoid the femoral artery and vein, and the obturator nerve and fascial planes of the muscle layers were identified step by step. The needle was inserted parallel to the long axis of the probe. After confirming no blood upon aspiration, 15 ml of 0.375% ropivacaine was injected into the fascial plane between the adductor brevis and adductor magnus, as well as into the midportion of the adductor longus and adductor brevis muscles.

Anesthesia induction was performed with propofol at 1-2 mg/kg, sufentanil 10 µg, and remifentanil 1.5 µg/kg, followed by mask ventilation for 5 minutes. A laryngeal mask was inserted for mechanical ventilation. The ventilation mode selected was pressure-controlled with volume guaranteed, with FiO₂ at 45%, tidal volume (VT) 6-8 ml/kg, PEEP 4-6 cmH₂O, Iratio 1:2, and respiratory rate (RR) 12-20 breaths per minute. Anesthesia maintenance was achieved with a continuous infusion of propofol at 4-6 mg/kg/h and remifentanil at 0.1–0.3 µg/kg/min.

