5.0 Study the implementation process

After entering the room, intravenous access was established, and routine monitoring of ECG, NBP, and SpO₂ was performed. Based on group assignment, the same physician experienced in nerve blocks performed either the obturator nerve block or the pericapsular nerve group (PENG) block. Anesthesia was induced and maintained according to a standardized protocol. The same anesthesiologist, who was unaware of the group assignments, collected various study parameters and data.

6. Subject recruitment and protective measures

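### Does recording block procedure time and needle passes unblind the person who measures adductor strength?

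*Protocol*

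**What the plan says.** Section 4 sets the level of blinding: "This clinical study uses a single-center, randomized, single-blind, parallel controlled trial design". That sentence does not name the blinded party. Sections 5.0 and 12 come closest to doing so.

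- **Operator (Section 5.0):** "the same physician experienced in nerve blocks performed either the obturator nerve block or the pericapsular nerve group (PENG) block".
- **Collector (Section 5.0):** "The same anesthesiologist, who was unaware of the group assignments, collected various study parameters and data".
- **Collector (Section 12):** "It was collected by the same anesthesiologist who did not know the grouping situation".

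The endpoints that bear on the question are:

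- **Primary (Section 2.2.1):** "Percentage reduction in adductor muscle strength at 5, 10, 15, 20, 25, 30 minutes, and 3 hours post-administration".
- **Secondary, under safety (Section 2.2.2.2):** "Procedure time and number of needle passes". Duration of surgery is a separate item in Section 2.2.2.1, so procedure time here is reasonably read as the time taken by the block.

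Section 4.1.2 describes the two techniques. In the P group, "An out-of-plane technique was used, with the needle tip directed medially toward the pectenous muscle", and there is one injection target. In the O group the patient is supine "with the affected thigh abducted and externally rotated", the needle follows the long axis of the probe, and there are two injection targets.

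**The concern.** The worry runs in three steps. Needle passes can be counted only by someone who watches the block, or learned from someone who did. Watching the block shows the arm. Section 12 gives data collection to one person and makes no exception for any variable. Put together, these suggest that the person meant to be unaware must see the arm before the 5-minute strength reading.

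The stakes would be real. This anesthesiologist is the only person the protocol describes as unaware of group. The protocol does not describe the strength test. If it is a voluntary effort test (an assumption), a tester who knows the arm could affect the result through encouragement or positioning. All 7 primary readings follow the block, so a collector who had seen it would carry that knowledge into every one of them.

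**Working it through.** The protocol gives no figure to reproduce here. The check is to count the items involved and then ask whether the statements can all be true together.

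**1. Endpoint items that need observation during the block.** Section 2.2 lists adductor strength, obturator reflex, duration of surgery, surgeon satisfaction, patient satisfaction, adverse reactions, procedure time and needle passes: 8 items. Only procedure time and needle passes belong to the block itself: 2 of 8, both secondary.

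**2. Would watching the block reveal the arm?** Yes. Section 4.1.2 gives three visible differences: thigh position, needle approach relative to the probe, and number of injection targets (1 against 2). This part of the concern is correct.

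**3. Does any passage require the collector to watch?** No.
- Section 12 says the data were collected by this person. It does not say that the person times the block or counts passes as they happen. Gathering two figures that someone else noted also satisfies the sentence.
- Section 5.0 limits the collector to *various* parameters, which is not all of them.
- Section 9.2 has the investigator enter the trial process, safety data and efficacy assessment in the case report form.
- Section 10.1 makes participating physicians, in the plural, responsible for confirming the accuracy of the data entered. Neither 9.2 nor 10.1 reserves recording for the collector.

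**4. Is there an arrangement in which everything holds?** Suppose the physician doing the block notes its duration and the number of passes. The collector is elsewhere during the block, measures strength from 5 minutes afterwards, and takes over the two figures once the strength readings are done. Then one person has collected the data, that person is unaware of group while testing, the operator is someone else, and both block items are recorded. No sentence in Sections 2.2, 4.1.2, 5.0, 9.2 or 12 is violated.

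**5. What if the collector did watch?** The statements in Sections 5.0 and 12 that this person is unaware of group would be false. Watching the block would depart from the plan; it would not result from following it.

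**6. Must the collector be beside the block because of the measurement times?** A percentage reduction needs a starting value, and the first post-block reading is at 5 minutes. The protocol does not say when the starting value is taken or who takes it. A starting value taken before the block, with re-entry after the injection, fits every passage. The timing makes the logistics tight without requiring presence during the block.

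**The case for a change.** The strongest reply is that blinding has to be arranged at the bedside and no analysis plan can restore it afterwards. The protocol chose to say who collects the data, and it names nobody else. The operator is given only the task of performing the block. Section 9.2 does not separate block items from assessor items. With a first reading at 5 minutes and no statement that the collector is absent or screened, a busy single-center team could easily let one person do everything.

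Part of this stands. The protocol does not say who notes procedure time and needle passes, or where the collector is while the block is performed. The two figures might also hint at the arm if handed over before strength testing, since one technique has two targets and the other has one.

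The conclusion that the assessor is thereby shown the arm does not stand. It needs several steps that the document does not supply: that collecting means watching, that the collector is also the strength tester (likely, because no one else is named, but not stated), and that this person stays beside the patient throughout. Against these inferences stand two explicit statements that the collector is unaware of group, and the use of a different person to perform the block.

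**Conclusion.** The concern identifies missing operational detail and does not show an error in the plan. A team that follows Sections 5.0 and 12 as written keeps the collector unaware of group, and the primary comparison stays observer-blind. Who notes the two block items, and where the assessor stands meanwhile, are points that site procedures or case report form instructions ordinarily settle. The natural choice, the operator noting them, uses staff already present.

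The gap covers 2 of 8 endpoint items, both secondary. For the 7 primary readings, no passage shows blinding broken, and the protocol offers no figures from which a bias could be estimated.

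The conclusion rests on two assumptions: that the statements about the unaware collector are carried out in practice, and that the block figures are not passed to the strength tester before the readings they could influence. It does not depend on whether the collector is also the strength tester.

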6.1 Inclusion criteria

Aged 18 years or older: scheduled for TURBT for unilateral bladder tumor: able to understand and provide informed consent.

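### Section 12 compares the two arms with a paired t-test, although the arms hold different, unmatched patients

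*Protocol*

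**What the plan says.** Section 12 (Data analysis) assigns tests by type of data. For measurement data summarised as mean and standard deviation, "comparisons between groups were conducted using the paired t-test". Categorical data get a chi-square test and ordinal data a rank-sum test. Significance is P below 0.05.

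The primary endpoint (Section 2.2.1) is "Percentage reduction in adductor muscle strength at 5, 10, 15, 20, 25, 30 minutes, and 3 hours post-administration". It is a continuous quantity. Duration of surgery (Section 2.2.2.1) and procedure time (Section 2.2.2.2) are continuous too.

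The design statements are:

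- Section 4: a "single-center, randomized, single-blind, parallel controlled trial design".
- Section 4.1.1: eligible patients "were randomized in a 1:1 ratio to the experimental and control groups".
- Section 4.1.2: "Patients were randomly divided into two groups using a random number table".
- Section 5.0: the same physician "performed either the obturator nerve block or the pericapsular nerve group (PENG) block".
- Section 6.1: patients are "scheduled for TURBT for unilateral bladder tumor".

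**The concern.** A paired t-test analyses within-pair differences. It needs a defined partner for every observation and therefore equal numbers in the two columns. The protocol describes nothing that could supply such pairs: no matching, no crossover, and no left-right contrast within a patient.

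Carried out literally, the pairs would be whatever rows happen to stand side by side in the SPSS file. Sorting the file differently would change the p-value with no change in the data. If the arms differ in size, the surplus patients have no partner and drop out. If the analyst instead pairs each patient's post-block value with that patient's own baseline, the test no longer compares the arms, although the sentence says it is for comparisons between groups.

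At stake is the only test the protocol names that fits the primary endpoint. This is not a detail left for a statistical analysis plan: the protocol names a test, and that test contradicts its own design.

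**Working it through.** The protocol gives no sample size, effect size or standard deviation for this comparison, so there is no planned figure to reproduce. The arm sizes below are assumptions, as are normal outcomes with equal SDs and a two-sided level of 0.05.

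**1. Does the row order matter?** Let both arms have n patients and the same SD, and let r be the accidental correlation between the two columns as sorted. The variance of the paired differences is 2·SD²·(1 − r), so

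t(paired) = t(independent) / √(1 − r), with n − 1 degrees of freedom instead of 2n − 2.

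With unmatched patients, r is noise created by the sort order, with mean 0 and standard deviation 1/√(n − 1).

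For n = 30 and a correct p of exactly 0.050, t(independent) = 2.002 on 58 df. The SD of r is 1/√29 = 0.186, so 95% of orderings give r within about ±1.96 × 0.186 = ±0.364.

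- r = +0.364: t = 2.002/√0.636 = 2.51 on 29 df, p = 0.018.
- r = −0.364: t = 2.002/√1.364 = 1.71 on 29 df, p = 0.097.

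Shuffling the rows of one arm in simulated data (5,000 to 10,000 shuffles per setting) agrees:

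| n per arm | Independent p | Paired p, central 95% of orderings | Orderings below 0.05 |
|---|---|---|---|
| 20 | 0.050 | 0.013 to 0.108 | 40% |
| 30 | 0.050 | 0.017 to 0.095 | 39% |
| 40 | 0.050 | 0.021 to 0.090 | 43% |
| 60 | 0.050 | 0.025 to 0.083 | 43% |

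Repeat runs at n = 30 gave 0.018 to 0.098 with 42%, and 0.019 to 0.096 with 41%. The differences are simulation noise.

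**2. What if the result is not borderline?** The same shuffling at n = 30:

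| Independent p | Paired p, central 95% | Orderings below 0.05 |
|---|---|---|
| 0.20 | 0.12 to 0.27 | about 0% |
| 0.01 | 0.002 to 0.030 | about 100% |
| 0.001 | 0.0002 to 0.006 | about 100% |

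The reported p-value always moves; the verdict changes only near the threshold.

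**3. Error rate and power.** If an arbitrary pairing is fixed independently of outcome, the simulated type I error is 0.050 to 0.052. Power falls because the degrees of freedom are halved. Take the effect that gives the independent test 80% power and apply the paired critical value on n − 1 df to the noncentral t distribution: power is 77.0% (n = 15), 77.9% (n = 20), 78.6% (n = 30) and 79.2% (n = 50).

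**4. Will the arms be equal?** The protocol does not say whether the random number table is used in blocks. If it is not, the number allocated to one arm is binomial (N, ½), and

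P(equal arms) = C(N, N/2) / 2^N.

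This gives 0.125 (N = 40), 0.103 (N = 60), 0.089 (N = 80) and 0.073 (N = 120). At N = 60 the arms are therefore unequal with probability 1 − 0.103 = 0.897. The mean absolute difference is about √(2N/π) = √(120/3.1416) = 6.2, so about 6 patients would have no partner. Blocking would reduce this, but Section 6.3 allows withdrawal at any time, which can unbalance the arms again. With 30 against 29 values the paired routine stops with an error.

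**The case against.** The strongest reply is that the wording is a slip for the independent-samples t-test. It would probably come to light once the arms turned out unequal, and correcting it changes no patient and no data. That is plausible, but it does not make the text right. With equal arms nothing would stop the literal test from running.

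A second reply is that the damage is smaller than the borderline example suggests. This stands in part. Away from p = 0.05 the verdict survives any sort order, type I error is close to nominal under a pairing fixed in advance, and the power loss is small. However, the protocol fixes no pairing, so the order remains open to choice after the data are seen, and the near-nominal error rate does not cover that case.

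A third reply is that some consequences are conditional. This also stands. Patients are lost only if the arms are unequal, and the 90% figure needs both an unblocked table and the assumed N. Section 12 never names the primary endpoint either; the link rests on that endpoint being continuous. The inference is safe, because neither the chi-square nor the rank-sum rule is written for such data.

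**Conclusion.** The concern holds. The test named for between-arm comparison of continuous endpoints is incompatible with an unmatched parallel-group trial. With equal arms its p-value is not uniquely defined. At an assumed 30 per arm and a correct p of 0.050, it ranges from about 0.018 to 0.098 according to sort order. With unequal arms it cannot be computed on all patients.

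The fault is arbitrariness and possible loss of patients. It is not a demonstrated inflation of false positives, nor a large loss of power. The contradiction itself rests on no assumption; only its numerical size depends on the assumed n, normal outcomes with equal SDs and, for the unequal arms, unblocked allocation. Because it affects the only stated test that fits the primary endpoint, it must be corrected before analysis.

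**What to change.** In Section 12, replace the paired t-test for comparisons between groups with an independent two-sample comparison; a Welch t-test is a sound default. Report the difference in means with its 95% confidence interval.

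For adductor strength, an analysis of covariance is preferable: patient outcome as the response, arm as the factor and pre-block strength as the covariate. A percentage reduction already requires a reference measurement (taken here to be the pre-block value), so this should need no new data. The sentence should also say which of the seven time points, or which repeated-measures model across them, the comparison addresses, since changing the test does not settle that.

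Paired tests may remain for describing change within an arm, labelled as such.

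With the independent test, a given data set yields one p-value whatever the row order, unequal arms are allowed, and the pooled form has 2n − 2 degrees of freedom (58 rather than 29 at 30 per arm). The cost is a short edit to Section 12, with no extra patients, data or staff.

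### Section 12 fixes a paired t-test between two independent arms; replace it with an independent-groups model adjusted for pre-block adductor strength, which costs little and may gain precision

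*Protocol*

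**What the plan says.** Section 2.2.1 gives one primary endpoint: "Percentage reduction in adductor muscle strength at 5, 10, 15, 20, 25, 30 minutes, and 3 hours post-administration". A percentage reduction needs a pre-block strength for each patient, although the section lists only times after the block.

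Section 4 describes a "single-center, randomized, single-blind, parallel controlled trial design". Section 4.1.1 has patients "randomized in a 1:1 ratio to the experimental and control groups", and section 4.1.2 adds: "Patients were randomly divided into two groups using a random number table". Neither matching nor crossover is described anywhere.

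Section 12 then states, for continuous data, that "comparisons between groups were conducted using the paired t-test". It names no covariate. The significance rule is: "P-value of <0.05 was considered statistically significant". Sidedness is not stated.

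**The concern.** There are two linked problems, one firm and one a matter of efficiency.

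1. **The named test does not match the design.** A paired t-test needs a defined partner for each observation. With two independently randomised arms there is none. Applied literally, the test would need equal arm sizes, and its p-value would depend on an arbitrary ordering of patients.
2. **The comparison makes no use of baseline as a covariate.** Pre-block strength enters only as the denominator of the percentage. Dividing by baseline does not guarantee that the result is unrelated to the measured baseline. Any remaining relation stays in the error term of a t-test.

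The sentence has to be rewritten for the first reason. If only the word for the test is changed, precision that an already required value might recover is left unused.

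**Working it through.** The protocol gives no sample size, effect size, SD or baseline correlation, so there is no planned figure to reproduce. The design facts come from sections 2.2.1, 4, 4.1.1, 4.1.2 and 12. All other inputs below are assumptions, and two-sided 5% is assumed throughout.

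**Step 1: cost of pairing unrelated patients.** With n per arm, the expected variance of the mean difference is the same for both tests. The degrees of freedom fall from 2n - 2 to n - 1. At n = 30 that is 58 versus 29, with critical t 2.002 versus 2.045. Power at an assumed effect of 0.8 SD, from the noncentral t distribution:

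| n per arm | Independent t | Arbitrary pairs |
|---|---|---|
| 20 | 69.3% | 67.0% |
| 30 | 86.1% | 85.0% |
| 40 | 94.2% | 93.7% |

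Simulated type I error stays near 5% for both tests. The loss is modest; the main fault is that the pairs are undefined.

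**Step 2: why percentage reduction can still depend on measured baseline.** There are two routes.

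- *Measurement error in the denominator.* Take a true baseline of 100 and a post-block strength of 40, a reduction of 60%. If the baseline reads 90, the result is (90 - 40)/90 = 55.6%. If it reads 110, the result is (110 - 40)/110 = 63.6%.
- *Spared strength that does not scale with baseline.* If a fixed force F is spared and the block removes a share d of the rest, the reduction is d(1 - F/B). With d = 60% and F = 15, it is 48.0% at B = 75 and 52.8% at B = 125.

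If the spared part is a constant share s of each patient's strength, the true reduction is d(1 - s). This is free of B, so only the first route remains. The protocol gives nothing to decide between these cases.

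**Step 3: variance with and without adjustment.** For total N in two equal arms and within-arm correlation r between pre-block strength and percentage reduction:

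adjusted variance / unadjusted variance = (1 - r²) × (1 + 1/(N - 4))

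- At 30 per arm the second factor is 1 + 1/56 = 1.018. The ratio is 1.018 at r = 0, 0.91 × 1.018 = 0.93 at r = 0.3, and 0.75 × 1.018 = 0.76 at r = 0.5.
- Break-even |r| = √(1 - 1/1.0179) = 0.13 at 30 per arm. It is 0.16 at 20 per arm and 0.11 at 40 per arm.
- With a useless baseline (r = 0), variance rises by 6.2% at 10 per arm, 2.8% at 20, 1.8% at 30 and 0.9% at 60.

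**Step 4: power by simulation.** Assumptions: block depth 60% versus 72%, between-patient SD 15 points, log-normal baseline, multiplicative error on pre- and post-block strength, one post-block time. There were 6,000 replicates per setting (Monte Carlo SE about 0.6 points). Power at 30 per arm, independent t / ANCOVA, by baseline CV and measurement CV:

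| Spared strength | 25%, 10% | 25%, 20% | 35%, 10% | 35%, 20% |
|---|---|---|---|---|
| None | 0.82/0.82 | 0.70/0.71 | 0.82/0.81 | 0.71/0.71 |
| Proportional, 15% | 0.78/0.78 | 0.57/0.59 | 0.77/0.77 | 0.57/0.58 |
| Proportional, 30% | 0.69/0.69 | 0.38/0.43 | 0.67/0.67 | 0.39/0.41 |
| Fixed force, 15% of mean | 0.75/0.78 | 0.55/0.60 | 0.72/0.76 | 0.52/0.58 |
| Fixed force, 30% of mean | 0.60/0.70 | 0.34/0.44 | 0.51/0.65 | 0.30/0.39 |

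| Result | None or proportional | Fixed force |
|---|---|---|
| Change in power, 30 per arm (points) | -0.7 to +4.4 | +3.3 to +14.1 |
| Change in power, 20 to 50 per arm (points) | -1.2 to +5.1 | +1.6 to +14.1 |
| Within-arm r | 0.06 to 0.34 | 0.27 to 0.54 |
| Variance ratio, 30 per arm | 0.90 to 1.01 | 0.72 to 0.93 |

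ANCOVA type I error in 20,000 null replicates at 20, 30 and 50 per arm was 4.7% to 5.0%. Under the same data model at 30 per arm, arbitrary pairing lost 0.5 to 1.7 points against the independent t-test.

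**The case against.** The strongest reply is that only the word for the test is wrong. A plain independent-groups t-test would be valid, and covariates and repeated-measures models are commonly left to an SAP, which may exist. Pre-block strength is also not ignored, since it is the denominator of every analysed value. The gain rests on assumed inputs, and its upper end appears only if the spared strength is a fixed force, which nothing in the protocol supports.

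Much of this stands:

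- Adjustment is about efficiency, not bias, and the gain may be nil. Of the 12 settings with zero or proportional sparing, 6 show equal power to two decimals and one shows a small loss.
- The low cost depends on an unstated sample size. Below 20 per arm the loss can reach about 2 points of power.
- The cost was worked out for a single-time ANCOVA, not for the mixed model over seven times.

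It does not remove the point. The protocol does not leave the test to another document: section 12 fixes one, and it contradicts section 4. The sentence must therefore change, and the choice of replacement is lopsided. From 20 per arm upward the worst loss is about one point of power, against a possible gain of up to 14, with no extra data to collect.

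**Conclusion.** The point holds. The paired t-test is wrong for two independent arms and must be replaced. That error by itself costs little power (about 0.5 to 2.3 points at 20 to 40 per arm) and leaves type I error near 5%, but it makes the analysis arbitrary as written.

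Using pre-block strength as a covariate in the replacement is advisable rather than essential. At 30 per arm the change in power runs from -0.7 to +14.1 points, depending on measurement error and on whether spared strength scales with baseline. These figures rest wholly on assumed effect, SD, CVs and sample size, so they show the range of possible outcomes and are not a forecast for this trial.

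**What to change.** In section 12, replace the paired t-test for the primary endpoint with an independent-groups model:

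- **If one time is named as primary:** ANCOVA at that time, with treatment as factor and pre-block adductor strength as covariate.
- **If all seven times are kept:** a repeated-measures mixed model with treatment, time, treatment-by-time, baseline and baseline-by-time.
- **Reporting:** keep percentage reduction as the scale and give the adjusted between-group difference with its 95% CI.
- **Section 2.2.1:** state when the pre-block strength is measured.

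For the other continuous endpoints, name an independent-groups test in place of the paired one.

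The cost is two or three sentences in section 12 and a clause in section 2.2.1. No new measurement is needed. The single-time ANCOVA uses one degree of freedom and, from 20 per arm upward, loses at worst about one point of power in the simulated settings.
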